11.3 Central Review Committee

An independent, Central Review Committee (CRC) will be used to reduce the variability between investigators in assessing scans and to minimize potential bias. The CRC will assess a subset of scans for prospectively-enrolled patients at each site. The CRC will review these scans and provide assessments including, but not limited to, lesion details at baseline, outcome of ablation, and lesion recurrence/progression during the post-ablation period.

As this is a SOC registry, assessments by the Principal Investigator (PI) will be used for all treatment decisions, as well as all protocol-defined analyses. Review by the CRC will be compared, where applicable, to the assessments made by the PI. The results of these comparisons will be summarized in separate analyses as part of the Clinical Study Report (CSR) and/or publication(s).

12.0 REGISTRY SCHEDULE

The Schedule of Assessments, which is found at the end of the Protocol Summary, serves as a guideline for participating sites regarding data to be collected for this registry. All should closely reflect standard of care.

12.1 Visit 1 – Screening

The screening assessments for this visit may occur over several dates within 60 days prior to Visit 2. If the patient is not seen within a 60 day window of the Ablation Day (Visit 2), the Screening Visit may occur on the same day as the ablation procedure.

Patients will be selected for microwave ablation based on the pre-procedure investigations and the Investigator's opinion. Eligible patients will be provided with the registry information, including the ICF.

The following screening assessments will occur within 60 days prior to the ablation visit (Visit 2):

- Patients must be given ample time to review and sign the ICF, or have a waiver in place, where applicable.
- Collect demographic information (age at time of Visit 1, sex, race, ethnicity).
- Collect patient parameters, as outlined in Section 19.1, subsection 2.
- Perform a liver tissue assessment (if available): steatosis (mild, moderate, severe); fibrosis/cirrhosis (mild, moderate, severe; include pathology results and fibrosis stage, if known); liver stiffness (actual stiffness value in kilopascals, if known); vascular invasion (presence or absence); microsatellite instability (MSI; high [MSI-H], low [MSI-L], or microsatellite stable [MSS]).
- BCLC staging, if applicable

- Evaluate Eastern Cooperative Oncology Group classification (ECOG) performance status.
- Body Mass Index (BMI): height and weight.
- Child-Pugh Score, if applicable and American Society of Anesthesiologists (ASA) Score.
- SOC imaging used to determine the ablation plans (CT, MRI, PET, Ultrasound (US), and/or X-ray), even if not within the screening window, should be used to determine soft tissue liver lesion details (e.g., lesion size, lesion type, location, shape).
 - If a Screening Visit occurs and the patient's SOC scans do not fall within the screening window, then an additional scan is not required for the screening visit.
 - For purposes of this Registry, target lesions are defined as any lesions ablated or intended to be ablated on the Ablation Day (Visit 2). Non-target lesions are defined as any lesions not ablated or not intended to be ablated on the Ablation Day (Visit 2).
 - All SOC scans of the abdomen/liver (CT, MRI, and/or PET) should be submitted to the Sponsor.
- Laboratory tests if applicable, per site SOC; to be done within 60 days of the ablation procedure,
 - Coagulation tests, including, INR, PT and APTT (or PTT).
 - Liver function tests, including AST, ALT, GGT, albumin, direct and total bilirubin, and total protein.
 - Renal function tests, including BUN, creatinine and electrolytes (sodium, potassium, chloride and bicarbonate).
 - Complete blood count (CBC), including differential cell count and platelet count.
 - Genetic markers including: Alpha-fetoprotein (AFP) level, Carbohydrate antigen 19-9 (CA19-9) level, Carcinoembryonic antigen (CEA).
- Review inclusion and exclusion criteria.
- Record all relevant medications taken within 60 days prior to Visit 2: Relevant concomitant medications include: chemotherapy, immunotherapy, blood-thinning or coagulation, NSAIDs, those used for hepatitis (if concurrently treating), and any others that are relevant in the opinion of the investigator.

12.2 Visit 2 – Ablation Procedure

Patients will be under anesthesia during the procedure per the site's SOC. On the day of ablation, SOC imaging will be done at the timepoints listed in the section below.

Pre-ablation

Data collected before the procedure:

- Evaluate ECOG performance status (prior to ablation).

- Confirm that the patient still meets inclusion and exclusion criteria.
- Record all relevant concomitant medications: Relevant concomitant medications include: chemotherapy, immunotherapy, blood-thinning or coagulation, NSAIDs, those used for hepatitis (if concurrently treating), and any others that are relevant in the opinion of the investigator.
- QOL questionnaires, using EORTC QLQ-C30 and liver-specific QLQ-HCC18. The questionnaires may be administered up to 72 hours prior to the ablation procedure. The questionnaires may also be administered over the phone, as needed.
- Pain score, using the Numeric Pain Rating Scale. The questionnaire may be administered up to 72 hours prior to the ablation procedure. The questionnaire may also be administered over the phone, as needed.
- SOC imaging (i.e. CT, MRI, US) to determine soft tissue liver lesion details (e.g. size, location, shape, stage), if performed as part of site's routine SOC.

During ablation

Use SOC imaging to guide the microwave ablation probe to the target soft tissue liver lesion(s) and insert the probe into the lesion(s). Data collected during the procedure:

- Record ablation procedure details as outlined in section 19.1, subsection 1
- Record any applicable AEs/SAEs.

Note: When available, some of the above ablation procedure details will be provided to the site via a report generated from the Call Home Database. The site will review the Call Home report and enter the procedure details into the clinical database, as applicable.

Post-ablation

After the ablation procedure, the following assessments will occur:

- Pain score using the Numeric Pain Rating Scale. The post-ablation pain score must be administered on the day of ablation (Day 0). The questionnaire may be administered over the phone, as needed.
- Relevant concomitant procedures (i.e. liver or lesion-related).
- Record all applicable AEs/SAEs and product complaints.
- Imaging to evaluate technical success, defined as ablation of the target lesion(s) according to the protocol and covered completely, with an adequate margin, as defined by the physician performing the ablation (that is, the ablation zone completely overlaps or encompasses the target lesion plus an ablative margin), as assessed by CT, MRI, PET, US, and/or X-ray, immediately following the procedure.
- Length of hospital stay, measured from post-ablation to discharge.
- Record Healthcare provider parameters as outlined in section 19.1, subsection 3
- Record any remaining ablation procedure details

- Record all relevant concomitant medications: Relevant concomitant medications include: chemotherapy, immunotherapy, blood-thinning or coagulation, NSAIDs, those medications used to treat AEs, those used for hepatitis (if concurrently treating), and any others that are relevant in the opinion of the investigator.

Note: All SOC scans of the abdomen/liver on the day of ablation (CT, MRI, PET, and/or US) should be submitted to the Sponsor.

12.3 Post-ablation Follow-up Visits

The list of assessments is the same for all follow-up visits unless otherwise specified.

At each follow-up visit, the patient will visit the site (or have a tele-visit and/or phone visit when unable to visit the site) and the following assessments will occur:

- Evaluate ECOG performance status (Visit 3 only). After Visit 3, evaluate ECOG, if applicable per site SOC. ECOG may be assessed over the phone.
- Laboratory tests, as follows, if applicable per site SOC:
 - Coagulation tests, including, INR, PT and APTT (or PTT).
 - Liver function tests, including AST, ALT, GGT, albumin, direct and total bilirubin, and total protein.
 - Renal function tests, including BUN, creatinine and electrolytes (sodium, potassium, chloride and bicarbonate).
 - CBC, including differential cell count and platelet count.
 - Genetic markers including: Alpha-fetoprotein (AFP) level, Carbohydrate antigen 19-9 (CA19-9) level, Carcinoembryonic antigen (CEA).
- Record all relevant concomitant medications: Relevant concomitant medications include: chemotherapy, immunotherapy, blood-thinning or coagulation, NSAIDs, those medications used to treat AEs, those used for hepatitis (if concurrently treating), and any others that are relevant in the opinion of the investigator. Relevant concomitant medications may be assessed over the phone.
- QOL questionnaires, using EORTC QLQ-C30 and liver-specific QLQ-HCC18, (Visits 3 through 6). The questionnaires may be administered over the phone, as needed.
- Pain score using the Numeric Pain Rating Scale (Visit 3 only). The questionnaire may be administered over the phone, as needed.
- Technique efficacy evaluation (Visit 3 only).
- Imaging to determine whether there has been a local or regional recurrence of lesion(s). If there is a recurrence, determine soft tissue liver lesion details via CT, MRI, PET, US, and/or X-ray.
 - All SOC scans of the abdomen/liver (CT, MRI, and/or PET) should be submitted to the Sponsor.
- Record relevant concomitant procedures (i.e. liver or lesion-related). Relevant concomitant procedures may be assessed over the phone.

- Record follow-up post-ablation treatment, including the number of successful repeat ablations, if applicable, and if patient has been hospitalized since the procedure. If patient has been re-ablated with NeuWave, record ablation procedure details as outlined in section 19.1, subsection 1.
- Record all applicable AEs/SAEs and product complaints. Assessments for safety may be assessed over the phone.
- Record date of registry completion, when applicable.

Note: in the case a patient has a liver resection or liver transplant, he/she should continue to be followed in the study, as outlined per the study protocol. Post-ablation follow-up visits should occur as per site SOC.

12.4 Unscheduled Visits

The following data will be collected during each unscheduled visit:

- Reason for the unscheduled visit.
- AEs/SAEs, if applicable.
- If applicable, SOC imaging to determine whether there has been a local or regional recurrence of lesion(s). If there is a recurrence, determine soft tissue liver lesion details via CT, MRI, PET, US, and/or X-ray.
 - All SOC scans of the abdomen/liver (CT, MRI, and/or PET) should be submitted to the Sponsor.
- Any follow-up post-ablation treatment, including the number of successful repeat ablations, if applicable, and if patient has been hospitalized since the procedure. If patient has been re-ablated with NeuWave, record ablation procedure parameters as outlined in section 19.1, subsection 1 and product complaints, as applicable. Upload of SOC images on the day of re-ablation with NeuWave should follow the requirements of upload per Visit 2 – Ablation Procedure.
- Any updates to the relevant concomitant medications and relevant concomitant procedures

13.0 ASSESSMENT OF SAFETY

Patients will be assessed and monitored for all AEs that are deemed at least unlikely related to the procedure or device from the day of ablation (from the time of first probe insertion) through the 5-year follow-up visit and all SAEs.

13.1 Adverse Events

Definitions

Adverse Event

For this registry, an adverse event is defined as any undesirable clinical occurrence (sign, symptom, or disease) in a patient. Only AEs that are deemed at least unlikely-related to the procedure or device will be collected. All SAEs, regardless of relationship to the study device or procedure, will be collected.

Expected Morbidity / Anticipated Adverse Events

An expected morbidity/procedural complication is defined as an AE that is known to be common or usual in nature, severity, or incidence during ablation of the liver.

Serious Adverse Event

All SAEs, regardless of relationship to the study device or procedure will be collected. It is the Investigator's responsibility to determine the "seriousness" of an AE using the protocol defined terms, listed below. An SAE is an AE that results in one or more of the following for this registry:

- Resulted in death: An AE that resulted in the patient's death.
- Life-threatening illness or injury: The patient was at imminent risk of dying at the time of the adverse event.
- Permanent impairment: An AE that resulted in permanent impairment of a body function or permanent damage to a body structure.
- Required in-patient or prolonged hospitalization.
- Resulted in medical or surgical intervention to prevent life threatening illness or injury or permanent impairment to a body or body function.
- Led to fetal distress, fetal death or congenital abnormality or birth defects.

Notes:

1. Progression of the disease under study should not be reported as an SAE.
2. "Death" should not be reported as an AE. The cause of death should be reported as an AE. The only exception is "Sudden Death" when the cause is unknown.
3. Planned hospitalization for a pre-existing condition is not considered an SAE.

SEVERITY OF ADVERSE EVENTS

It is the Investigator's responsibility to assess the severity of an AE. A change in severity may constitute a new reportable AE.

Also, the following guideline should be used to determine the severity of each adverse event:

- **MILD:** Awareness of signs or symptoms, but does not interfere with the patient's usual activity or is a transient event that resolves without treatment and with no sequelae.
- **MODERATE:** A sign or symptom, which interferes with the patient's usual activity.
- **SEVERE:** Incapacity with inability to do work or usual activities.

RELATIONSHIP OF ADVERSE EVENTS

It is the Investigator's responsibility to assess the relationship between all AEs to the registry device and procedure. All SAEs, regardless of relationship to the study device or procedure will be collected. Adverse events deemed to have an unlikely, possible, probable, or causal relationship to the procedure or device should be captured in source as part of the study and entered in the the AE eCRF. Adverse events deemed to be not related to the procedure or device should only be captured in source. The following guidelines should be used in determining the relationship of an AE to a device, procedure, or other causality:

Not related	
Relationship to the procedures or device can be excluded when:
 
 • The event is not a known side effect of the product category the device belongs to or of similar device and procedures; • The event has no temporal relationship with the use of the device or the procedures; • The event does not follow a known response pattern to the device (if the response pattern is previously known) and is biologically implausible; • The discontinuation of the device application or the reduction of the level activation/exposure (when clinically feasible) and reintroduction of its use (or increase of the level of activation/exposure), does not impact on the event; • The event involves a body-site or an organ not expected to be affected by the device or the procedure; • The event can be attributed to another cause (e.g. an underlying or concurrent illness/clinical condition, an effect of another device, drug, treatment, or other risk factors); • Harms to the subject are not clearly due to use error; or • To establish the non-relatedness, not all the criteria listed above might be met at the same time, depending on the type of device/procedure and the event.
Unlikely*	
The relationship with the use of the device seems not relevant and/or the event can be reasonably explained by another cause, but additional information may be obtained.

Possible*	The relationship with the use of the device is weak but cannot be ruled out completely. Alternative causes are also possible (e.g. an underlying or concurrent illness/condition and/or an effect of another device, drug, or treatment). Cases where relatedness cannot be assessed, or no information has been obtained should also be classified as possible.
Probable*	The relationship with the use of the device seems relevant and/or the event cannot reasonably be explained by another cause, but additional information may be obtained.
Causal Relationship*	
The event is associated with the device or with procedures beyond reasonable doubt when:
 
 • The event is a known side effect of the product category the device belongs to or of similar device and procedure • The event has a temporal relationship with the device uses/application or procedures • The event involves a body-site or organ that 
 ○ The device or procedures are applied to ○ The device or procedures have an effect on • The event follows a known response pattern to the medical device (if the response pattern is previously known) • The discontinuation of medical device application (or reduction of the level of activation/exposure) and reintroduction of its use (or increase of the level of activation/exposure), impact on the event (when clinically feasible) • Other possible causes (e.g. an underlying or concurrent illness/clinical condition and/or an effect of another device, drug, or treatment) have been adequately ruled out • Harm to the subject is due to error in use • To establish the relatedness, not all the criteria listed above might be met at the same time, depending on the type of device/procedure and the event.

*Denotes “related” to the procedure or device and should be captured (AE) as part of the study.

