7.7 Removal of Patients from the Registry

In accordance with the current revision of the Declaration of Helsinki and the Code of Federal Regulations, a patient has the right to withdraw from the registry at any time for any reason without prejudice to his/her future medical care by the physician or the institution. Should a patient (or patient's legally authorized guardian/representative) decide to withdraw from the registry, all efforts will be made to collect all AEs the patient may have experienced.

Participation may be terminated prior to completing the registry for any of the reasons listed below (reasons that do not fit the categories below will be documented as "other").

Withdrawal of Consent:

If a patient chooses to withdraw early from the registry, the patient should contact the site, which will then complete the Subject Completion/Discontinuation eCRF page. When a patient's participation is terminated prior to completing the registry, the reason for withdrawal is to be documented on the eCRF and in the source documentation.

Investigator Decision for Patient Termination:

The Investigator may withdraw a patient for any safety reason, including, but not limited to, the following reasons:

1. Inability of Investigator to locate and target the soft tissue liver lesion.
2. Inability of patient to tolerate the anesthesia.

Note: If a patient experiences an AE during probe puncture and is not ablated, this patient should be followed until AE resolution. If no AE occurred during probe puncture and the patient could not be ablated, the patient should be discontinued.

Death:

When available, the cause of death should be documented in the AE eCRF. The Subject Completion/Discontinuation eCRF also must be completed.

Lost to follow-up:

All patients should be encouraged to return for clinic visits for evaluation during the registry follow-up period. After all attempts to contact the patient have failed and after 2 consecutive missed visits to the site, a patient will be considered lost to follow up. Should the patient return to the site, their status in the database may be updated accordingly and data continue to be collected. For patients who are definitively lost to follow-up, the reason for early termination will be completed in the Subject Completion/Discontinuation eCRF.

Site Termination or Registry Termination:

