8.13 Safety Analyses

All AEs reported during the study will be coded to the Medical Dictionary for Regulatory Activities (MedDRA). All AEs will be summarized by MedDRA system organ class (SOC) and preferred term (PT). Separate summaries will be provided for device-related and procedure-related AEs. Serious AEs will be summarized in a similar manner. All reported adverse events will be listed.

Ninety-five percent confidence intervals may be provided for pre-specified adverse events of interest, which are:

- Ascites (accumulation of fluid causing abdominal swelling)
- Biloma/bile leak (buildup of bile within the abdomen)/bile leak)
- Bile duct injury
- Bleeding requiring transfusion, embolization (obstructing of blood vessel or organ to stop bleeding), or prolonged hospital stay
- Intrahepatic hematoma
- Pneumothorax and hemothorax
- Organ injury other than the liver (such as gastrointestinal injury/perforation, diaphragmatic injuries/hernia)
- Fever
- General feeling of tiredness
- Infection
- Liver dysfunction
- Liver abscess
- Nausea
- Pain
- Pneumonia
- Pleural effusion

- Post ablation syndrome, which is your body's response to the destroyed lesion. You may experience flu-like symptoms, including fever, decreased appetite, and general discomfort. This syndrome generally happens 3 to 5 days after the ablation procedure.
- Skin burn
- Thrombosis (local coagulation or clotting of the blood in the circulatory system, with/without tube drainage)
- Tumor implantation

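### Protocol 13.1 and 7.7 give conflicting instructions for recording a death from progression, so the all-SAE and fatal-SAE totals can mix reporting conventions

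*Protocol*

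**What the plan says.** Five provisions of the protocol bear on a death from progression of the disease under study.

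- Protocol 13.1, Serious Adverse Event, Note 1: "Progression of the disease under study should not be reported as an SAE". It does not say whether fatal progression is included.
- Protocol 13.1, Note 2: "The cause of death should be reported as an AE". Its one exception is sudden death of unknown cause.
- Protocol 7.7, Death: "When available, the cause of death should be documented in the AE eCRF". The Subject Completion/Discontinuation eCRF is also completed; the protocol does not say that this form has a field for cause of death.
- Protocol 13.1, seriousness list: "Resulted in death: An AE that resulted in the patient's death". For scope, "All SAEs, regardless of relationship to the study device or procedure, will be collected".
- Protocol 13.1, Relationship of Adverse Events: "Adverse events deemed to be not related to the procedure or device should only be captured in source".

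On the analysis side, the incidence of reportable AEs and all SAEs through the end of the study is secondary endpoint 6 (Protocol 6.3, SAP 8.4.2). SAP 8.6 and 8.13 summarize AEs by system organ class and preferred term, and "Serious AEs will be summarized in a similar manner". Neither section says how progression is to be treated. SAP 8.7 plans no sensitivity analysis, and SAP 8.9 marks site homogeneity as not applicable.

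**The concern.** Consider a patient who dies of liver tumour progression at month 30. One site follows Note 2 and the seriousness list and enters a fatal SAE. A second follows Notes 1 and 2 and enters a non-serious AE. A third follows Note 1, judges the event unrelated, and leaves it in source. Each can point to protocol text in support.

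Secondary endpoint 6 runs for five years in a population with liver tumours, so deaths from the disease may be a sizeable share of all serious outcomes. If sites differ, the all-SAE total, and any count of fatal SAEs drawn from the same records, reflects local reporting habit as well as patient experience. Comparisons by site, by enrolment route, or with outside series would carry that artefact. Retrospective patients fall under the same collection rules (Protocol 13.2), so no enrolment route is exempt.

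**Working it through.** The plan states no SAE rate, so there is no figure to reproduce. The check has two parts.

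**1. Do the provisions fit together?** The table sets the three possible records of a death from progression against the provisions as written.

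| Record made by the site | Note 1 | Note 2 and 7.7 | Resulted-in-death criterion | Source-only rule, if judged unrelated |
|---|---|---|---|---|
| Fatal SAE | broken | met | met | not engaged: all SAEs are collected |
| Non-serious AE on the AE eCRF | met | met | broken, unless Note 1 is read as an exception to it | broken |
| Nothing on the AE eCRF | met | broken | broken, unless Note 1 is read as an exception to it | met |

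No row is clean. Notes 1 and 2 on their own can both be met, by a non-serious AE. The conflict comes from adding the seriousness criterion and, for events judged unrelated, the source-only rule. Protocol 13.2 records seriousness for each event, so a site has to take a position. No section ranks the provisions.

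Rating the event as unlikely related avoids the source-only rule. However, the footnote to the relationship table counts unlikely as related, so a disease death could then appear in the device- or procedure-related summaries of SAP 8.13.

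**2. How much could it matter?** This part is illustrative, because the inputs are assumptions and not figures from the documents.

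- b = share of patients with at least one other SAE: 10% to 30%
- f = share of patients with fatal progression: 10% to 40%
- s = share of fatal progressions that sites report as SAEs: 0 to 1
- fatal progression and other SAEs are taken as independent

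SAE incidence = b + (1 − b) × f × s

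The difference between all sites reporting (s = 1) and none (s = 0) is (1 − b) × f.

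- Smallest: (1 − 0.30) × 0.10 = 0.07, or 7 percentage points
- Largest: (1 − 0.10) × 0.40 = 0.36, or 36 percentage points

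| b | f | s = 0 | s = 0.5 | s = 1 |
|---|---|---|---|---|
| 20% | 10% | 20% | 24% | 28% |
| 20% | 40% | 20% | 36% | 52% |

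At 1,500 patients, 7 and 36 points are 1500 × 0.07 = 105 and 1500 × 0.36 = 540 patients. If patients with fatal progression are more likely than others to have another SAE, the difference is smaller than this. A count of fatal SAEs has no such cushion: it would move by f itself, 10 to 40 points.

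**The case against.** The strongest answer is that the Notes sit directly under the seriousness list and work as exceptions to it. Note 3 plainly does so, taking planned hospitalization out of the hospitalization criterion. Read the same way, Note 1 overrides the death criterion, and Note 2 mainly governs which term to enter. A non-serious AE would then satisfy both. This is a fair reading, and it disposes of any claim that Notes 1 and 2 flatly contradict each other. It does not settle the matter. Note 1 does not mention fatal progression, and a non-serious AE judged unrelated is still kept off the AE eCRF by the source-only rule, against Note 2 and 7.7.

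The wording is also softer than a strict rule: the provisions say should, and 7.7 adds a condition of availability. AE entries alert the sponsor (13.2) and monitors review eCRFs (16.0), so a common convention may exist in eCRF instructions or in the separate table shells, which are not available here. Variation between sites is therefore possible but not demonstrated.

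Two stronger inferences are tempting and are not supported.

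- A reader might conclude that the SAE results cannot serve as a safety measure at all. The all-SAE total was never specific to the procedure, since SAEs are collected whatever their relationship. SAP 8.13 gives separate device- and procedure-related summaries, tabulates by preferred term and lists every event. Rows for other specific complications stay readable, and progression entered under its own term is visible.
- A reader might assume five-year mortality of 40–60% with 60–80% of deaths from disease, and conclude that 1500 × 0.40 × 0.60 = 360 to 1500 × 0.60 × 0.80 = 720 patients change SAE status. The documents contain neither percentage, and the sum ignores patients who are already counted for another SAE.

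**Conclusion.** The concern holds, limited to the totals. As written, Note 1, Note 2 with section 7.7, the resulted-in-death criterion and the source-only rule for unrelated AEs cannot all be met for a death from progression, and nothing says which prevails. The all-SAE and fatal-SAE totals under secondary endpoint 6 can therefore mix reporting conventions, and the SAP has no rule that would bring them into line.

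The size is illustrative: a difference of about 7 to 36 percentage points in SAE incidence between the two extremes of reporting. It rests on the assumed ranges and independence given above; a partial mix of conventions gives less.

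Overall survival and recurrence-free survival use death from any cause (SAP 8.6), and the completion/discontinuation form is filled in at death, so they need not be affected. The primary endpoints do not depend on SAE coding. The problem is worth correcting because it affects a named secondary endpoint and the correction is cheap.

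**What to change.** **Protocol.** Reconcile Notes 1 and 2 of 13.1, the resulted-in-death criterion, the source-only rule for unrelated AEs and section 7.7, so that death from progression of the disease under study is recorded one way at all sites. Which way is the sponsor's choice. If the completion/discontinuation form is to carry the cause, first confirm that it has a field for it.

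**SAP 8.6 and 8.13.** Prespecify a list of preferred terms that denote progression of the disease under study. Tabulate SAEs and fatal SAEs with those terms excluded, whether they were entered as serious or not. Show deaths from progression in a separate row. Records already entered under either convention are then handled alike.

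**Cost.** One derived flag, a short protocol clarification, and queries for deaths with no cause entered. The flag cannot recover deaths for which nothing was put on the AE eCRF. Where a query does not establish the cause, report the death in a row for cause not recorded. No endpoint, visit or sample size changes.
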